8.3 Interim Analyses

No interim analyses will be conducted.

9 RESPONSIBILITIES OF THE INVESTIGATOR

9.1 Good Clinical Practice

Investigators must adhere to the procedures outlined in this Study Protocol. The procedures set out in this study protocol, pertaining to the conduct, evaluation, and documentation of this study, are designed to ensure that the Investigators and CRO abide by GCP as described in the ICH Guidelines Topic E6: "Guideline for Good Clinical Practice." Compliance with these regulations also constitutes compliance with the ethical principles described in the current revision of the Declaration of Helsinki. The study will also be carried out in keeping with local legal and regulatory requirements.

9.2 Ethics

The appropriate IRB must review the Study Protocol and the Informed Consent Form prior to initiating the study. Any significant modifications to the IRB-approved protocol or informed consent must be made in consultation with the IRB.

9.3 Confidentiality of Subjects

Any information that identifies subjects with respect to this research study will be kept confidential. However, records identifying the subject may be inspected by representatives of the IRB, the Clinical Research Organization (or its designate) if applicable, and/or the FDA. Subjects' identity will remain strictly confidential during all record reviews, as well as in any publication that may result from this research. Subjects will be identified by study code only; their names will not be used.

ACZ1601 (01JUN2016) Page 11 of 14

9.4 Informed Consent

Informed consent is a process that is initiated prior to the individual's agreeing to participate in the study and continuing throughout the individual's study participation. Appropriate discussion of risks and possible benefits of this therapy will be provided to the subjects. Consent forms describing in detail the study interventions/products, study procedures and risks will be given to the subject and written documentation of informed consent is required prior to starting intervention/administration study product. Consent forms will be IRB approved and the subject will be asked to read and review the document. Upon reviewing the document, the investigator will explain the research study to the subject and answer any questions that may arise. The subjects will sign the informed consent document prior to any procedures being done specifically for the study. The subjects should have the opportunity to discuss the study with their surrogates or think about it prior to agreeing to participate. The subjects may withdraw consent at any time throughout the course of the trial. A copy of the informed consent document will be given to the subjects for their records. The rights and welfare of the subjects will be protected by emphasizing to them that the quality of their medical care will not be adversely affected if they decline to participate in this study.

9.5 Data Handling and Record Keeping.

Investigators must ensure that proper source documentation for all study activities are diligently maintained and securely kept. Investigators will transfer all relevant data from source documents to the Case Report Form as stipulated in this Study Protocol and his/her signature on the Case Report Form guarantees completeness and integrity of these data. Investigators will maintain reliable study device dispensing/dosing records and will store study supplies in a secure, locked location. In addition, Investigators will ensure that all study-related source documentation and Case Report Forms will be maintained for a period of two years after the conclusion of the study.

9.6 Direct Access to Source Data/Documents

Investigators must ensure that institutional regulations and the Informed Consent Form clearly permit study-related monitoring, audits, IRB review, and regulatory inspections providing direct access to source data and documents.

10 SUPPLEMENTS

I Prohibited Medications / Wash-Out Periods

SUPPLEMENT I Prohibited Medications / Wash-Out Periods

Use of the following medications (concurrent and contraindicated treatments) are prohibited during the course of the study and appropriate wash-out periods must be respected:

100 C	Medication	Washout
Topical	Retinoids, antibiotics, BPO, dapsone, bleaching agents	2Weeks washout prior to V1
ОТ	C acne medications or bleaching agents	1Week washout prior to V1

Oral Antibiotics for acne	4Weeks washout prior to V1
Oral Retinoids	24Weeks washout prior to V1
Cryotherapy, chemical peels, microdermabrasion	2Weeks washout prior to V1
Laser Resurfacing and dermabrasion	24Weeks washout prior to V1
Investigational Drugs	4Weeks washout prior to V1

ACZ1601 (01JUN2016) Page 13 of 14

SUPPLEMENT II

Patient's Preference Questionnaire

The aim of this questionnaire is to find out what you like and what you don't like about different types of skin medications that you have used.

1. For all skin medicines you have used in the past, please rate the following treatments in the order you preferred them:

(1= "liked the best", 2= "second best", 3= "third best", 4= "fourth best, 5= "liked the least". If you have not used a certain type of skin medicine, please enter N/A for does not apply to me.)

Gel Lotion Cream Ointment Spr	ray
-------------------------------	-----

2. Please rate the following qualities of the gel, compared to the other skin medicines you have used in the past

(If you have not had a previous experience with other skin medicines, please circle N/A for does not apply to me.)

	Very Inferior "Much Worse"	Inferior "Worse"	About the same	Better	Superior "Much Better"	Does Not Apply to Me
Gel is easy to use	1	2	3	4	5	N/A
I am able to continue daily activities right away following putting the medicine on my skin (i.e., getting dressed, doing school work, playing etc.)	1	2	3	4	5	N/A
The gel leaves my skin feeling soft	1	2	3	4	5	N/A
I am able to apply the gel to large body surface areas	1	2	3	4	5	N/A
The gel disappears into my skin quickly when I apply it	1	2	3	4	5	N/A

3. Please rate the gel on each of the following:

	Very Poor	Poor	Fair	Good	Excellent	Does Not Apply to Me
Moisturizing ("It leaves my skin feeling soft and smooth")	1	2	3	4	5	N/A
Lack of residue ("There is nothing left on my skin")	1	2	3	4	5	N/A
Does not feel greasy	1	2	3	4	5	N/A
Absorbs quickly ("Disappears into my skin quickly after I put it on my skin")	1	2	3	4	5	N/A
Easy to apply	1	2	3	4	5	N/A
Fragrance-free ("Does not smell")	1	2	3	4	5	N/A
Spread ability ("Spreads easily on my skin")	1	2	3	4	5	N/A
Lack of stickiness ("No sticky feeling")	1	2	3	4	5	N/A

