1 GENERAL INFORMATION

1.1 Introduction

Truncal acne is an under diagnosed and under treated condition. Aczone gel 7.5% has already been approved for the treatment of acne vulgaris. However, topical treatment of truncal acne is very difficult in traditional vehicles due to the difficulty of covering large body surface areas. The recent approval of Aczone gel 7.5% foam gives us an opportunity to address this unmet need. Therefore, the current pilot study will investigate the efficacy and safety of Aczone 7.5% gel in the treatment of truncal acne.

Truncal acne is estimated to occur in 61 percent and 45 percent of acne patients, respectively. 1.2 The pathophysiology of truncal acne is the same as facial acne, and both respond similarly to therapy. However, despite a wide range of treatment options available, the management of truncal acne remains challenging. Clinicians tend to emphasize oral therapies over topical interventions for truncal acne as it is typically assumed oral medications are more convenient than applying topical applications to large and potentially hard-to reach body areas. This line of reason is based on using standard creams or gels and does not necessarily hold-up with the advent of foam formulations that are significantly more convenient in treating hard-to-reach areas and larger surface areas. In fact, foam vehicles are associated with improved usability, better adherence and, consequently, improved therapeutic results. 5,6,7,8,9,10,11,12 Aczone gel 7.5% has been approved by the FDA for the treatment of acne vulgaris in individuals who are older than 12 years of age. Aczone gel 7.5% have been used on the chest and back acne during the phase III clinical trials but its efficacy has not been an endpoint in this study. It is reasonable to assume that Aczone gel 7.5% could present to be a viable treatment option for truncal acne. The current pilot study will investigate the efficacy and safety of Aczone gel 7.5% in the treatment of truncal acne. Based on the recent phase III clinical study of aczone gel 7.5%, it is expected that the typical risk/benefit profile of aczone gel 7.5% should apply in the treatment of truncal acne (ie, reduction in acne signs and symptoms, with possible adverse effects such as burning, stinging, tingling, pruritus, dry skin, erythema and/or edema).

- 1. Thomas DR. Psychosocial effects of acne. J Cutan Med Surg. 2004;8 Suppl 4:3-5.

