3 STUDY DESIGN

This is a three-center, open-label pilot study ([name] Louisville, KY, [name], DO, Las Vegas, NV & [name] Sacramento, CA.). All study subjects will receive Aczone gel 7.5% at Visit 1. The duration of the study is 16 weeks and consists of a Screening, Baseline Visit, and three (3) Follow-up Visits at Weeks 4, 10, and 16.

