5.1.4 Visit 4 (Week 16; ± 5 days)

- Urine Pregnancy Test (if applicable)
- Concomitant Medication/Treatment
- Adverse Events
- Vital Signs
- Weight
- Assessments
 - Trunçal Acne IGA
 - Truncal Lesion Counts
 - Tolerability
- Collect Study Medication
- Patient preference questionnaire

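### Supplement II question 1 leaves unclear whether the study gel counts, merges it with earlier gels and makes no provision for one-vehicle subjects, so pooled gel ranks can be tilted upward and cannot be attributed to the study product

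*Combined protocol and SAP*

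**What the plan says.** - Supplement II, question 1, has the stem "For all skin medicines you have used in the past, please rate the following treatments in the order you preferred them". The types offered are gel, lotion, cream, ointment and spray, ranked from 1 (best liked) to 5 (least liked). Gel is one entry, and the study product is not named.
- For types not used, the instruction is "If you have not used a certain type of skin medicine, please enter N/A for does not apply to me".
- Question 2 compares the gel with other skin medicines and gives an opt-out: "If you have not had a previous experience with other skin medicines, please circle N/A for does not apply to me". Question 3 rates the gel by itself.
- Section 3: "All study subjects will receive Aczone gel 7.5% at Visit 1". In the assessment schedule (5.1.1) and in 5.1.4, the "Patient preference questionnaire" appears at Visit 4 (Week 16) only.
- Section 4.1 does not require earlier acne treatment. Supplement I asks only for a washout of earlier topical products, dapsone among them.
- Section 8.2 plans analyses of all enrolled subjects, means and standard deviations for continuous variables, frequencies for categorical ones, and inclusion of the questionnaire data. It does not say how N/A entries, differing numbers of ranked types or denominators are handled.
- Preference is not among the objectives (section 2), the primary endpoint (6.1) or the secondary endpoints (6.2).

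**The concern.** By Week 16 gel is the one vehicle that every treated subject has used. Each other type is ranked only by those who happened to use it earlier. Three problems follow.

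1. The stem can be read in two ways. Some subjects will count the study gel as used; others will take past use to mean before the study. Their answers then belong to different questions.
2. A subject who has used earlier gels has one box for both those and the study gel. The rank cannot be assigned to either.
3. A subject who has used only gel, and who ranks it, has nothing to rank it against. The natural entry is 1, which a frequency table counts as a preference.

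A statement that a given percentage of subjects liked the gel best would then combine real comparisons with automatic first places, and it would not be a statement about the study product.

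**Working it through.** The plan gives no preference figure to reproduce and no data on which vehicles subjects used before. The check therefore asks what question 1 would show if subjects had no preference at all. The gel-only share and the number of vehicles used are assumptions, shown as ranges.

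**Setting.** Suppose the study gel counts, ranks run consecutively from 1, and a subject has used k types including gel. With ranks assigned at random, P(gel first) = 1/k and the mean gel rank is (k+1)/2.

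| k | P(gel first) | Mean gel rank |
|---|---|---|
| 1 | 100% | 1.0 |
| 2 | 50% | 1.5 |
| 3 | 33.3% | 2.0 |
| 4 | 25% | 2.5 |
| 5 | 20% | 3.0 |

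Both columns depend on k with no preference present, so a raw rank does not mean the same thing in two subjects with different k.

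**Pooling over all subjects.** Let a share f be gel-only and the rest have used k types. Then P(gel first) = f + (1 − f)/k.

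| f (number of 30) | Rest k = 3 | Rest k = 2 |
|---|---|---|
| 0% (0) | 33.3% | 50% |
| 10% (3) | 40.0% | 55% |
| 20% (6) | 46.7% | 60% |
| 30% (9) | 53.3% | 65% |

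In counts, for f = 20% and k = 3: 6 automatic first places plus 24/3 = 8 by chance gives 14 of 30. For f = 30%: 9 + 21/3 = 16 of 30. Restricting to subjects with at least two types returns every row to 33.3% or 50%.

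**Variable exposure.** Let each of the four other types have been used independently with probability u. The gel-only share is (1 − u)^4. Gel's first-place share over all subjects is compared with that of any other type among its own users.

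| u | Gel-only | Gel first, all subjects | Other type first, own users | Difference (points) | Gel first, k ≥ 2 |
|---|---|---|---|---|---|
| 0.2 | 41% | 67.2% | 41.0% | 26 | 44.5% |
| 0.4 | 13% | 46.1% | 33.7% | 12 | 38.1% |
| 0.6 | 2.6% | 33.0% | 27.9% | 5 | 31.2% |
| 0.8 | 0.2% | 25.0% | 23.4% | 2 | 24.9% |
| 1.0 | 0% | 20.0% | 20.0% | 0 | 20.0% |

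Restricting to k ≥ 2 removes the automatic first places, but a gap of up to about 4 points remains (38.1 − 33.7 at u = 0.4) because k still varies. A pairwise percentage, study gel against one comparator among subjects who ranked both, is 50% under no preference whatever k is.

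**Merging study and earlier gels.** Suppose the study gel would be ranked first by 50%, and half of the answers in fact describe earlier gels. If earlier gels stand at 30%, the recorded figure is 0.5 × 50 + 0.5 × 30 = 40%. If they stand at 70%, it is 60%. This error has no fixed direction.

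**The case against.** A reader might infer that a subject with no other experience is forced to score gel as liked best, and that the gel result is therefore biased upward. The documents do not support either statement.

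- *Forced first rank.* Read literally, the stem allows a subject with no earlier skin medicine to enter N/A throughout and add no rank. The form does not require consecutive ranks starting at 1, and it labels 5 as least liked, so a gel-only or two-vehicle subject who disliked the gel could enter 5. In reply, the N/A instruction turns on not having used a type, which is untrue of gel for anyone treated, and this favours counting the study gel. The wording remains ambiguous; it does not compel an answer.
- *Settled upward bias.* The gel-only tilt, where gel is ranked first by default, can only raise gel's share, but its size depends on an unknown exposure pattern and may be zero. Merging with earlier gels can push either way. No single signed conclusion follows.
- *No defined preference result.* Section 8.2 names neither a percentage ranking gel first nor a mean rank. This stands. Even so, with all enrolled subjects analysed and no denominator rule, pooling is what the text implies.
- *Practical importance.* Ease of use on large areas is asked directly in question 2, with an opt-out for those lacking other experience, and ease of application in question 3. Both refer to the gel and do not depend on ranks. This also stands.
- *Foam.* Section 1.1 argues that "foam vehicles are associated with improved usability, better adherence and, consequently, improved therapeutic results", yet foam is not offered in question 1. That is a gap in coverage; it creates no tilt toward gel.

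**Conclusion.** The point holds as a minor one. Question 1 is ambiguous on whether the study gel counts, cannot separate it from earlier gels, and has no provision for one-vehicle subjects. If its ranks are tabulated over all subjects, the share ranking gel first can be tilted upward. With no preference and three vehicles used by the rest, the figure is 47% to 53% instead of 33% for an assumed gel-only share of 20% to 30%. Under the variable-exposure assumption, the gap between gel and another type runs from 0 to about 26 points. These figures assume that gel-only subjects rank gel and enter 1, and that ranks are consecutive. The failure to attribute the answer to the study product needs no such assumption: it follows from the single gel entry.

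The consequence is confined to an exploratory descriptive result in a 30-subject open-label pilot. The primary and secondary endpoints are untouched.

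**What to change.** In Supplement II, question 1:

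- Reword the stem to ask about all skin medicines used, including the study gel.
- List *Study gel* and *Other gel* as separate entries.
- Tell subjects to rank only the types they have used, consecutively from 1, with as many ranks available as there are items. Drop the fixed label of 5 as least liked, since the list now has six entries.
- Adding *Foam* is optional; it would answer the interest shown in section 1.1 but does not bear on the tilt.

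In section 8.2, state that question 1 is reported only among subjects who ranked the study gel and at least one other type, as the number and percentage preferring the study gel to each comparator, with the denominator for each. Do not average raw ranks.

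If the form can no longer be changed, restricting the denominator still removes the automatic first places, but it does not separate the study gel from earlier gels, and the report should say so.

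The cost is one reworded question and one table. The downside is a smaller denominator for each comparison (if 40% had used a given type, 12 of 30) and possibly a less favourable percentage.
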